HiSCR	Hidradenitis Suppurativa Clinical Response is defined as at least 50% reduction in AN count with no increase in abscess count and no increase in draining fistula count relative to baseline at each visit
[REDACTED]	[REDACTED]
HIV	human immunodeficiency virus

Abbreviations and Special Terms	Definition
HS	hidradenitis suppurativa
HS Pain NRS	Hidradenitis Suppurativa Pain Numeric Rating Scale
HS-PGIC	Hidradenitis Suppurative Patient Global Impression of Change
IB	Investigator's Brochure
ICF	informed consent form
ICH	International Conference on Harmonisation
ID	identification
IEC	independent ethics committee
[REDACTED]	[REDACTED]
IL	interleukin
IPL	intense pulsed light
IRB	institutional review board
IWRS	Interactive Web Response System
ITT	Intent to treat
JAK	Janus kinase
MedDRA	Medical Dictionary for Regulatory Affairs
Nd:YAG	Neodymium-doped yttrium aluminum garnet; Nd:Y ₃ Al ₅ O ₁₂
NRS	numeric rating scale
PGIC	Patient Global Impression of Change
P-gp	P-glycoprotein
[REDACTED]	[REDACTED]
PK	pharmacokinetic
QD	once daily
QTcF	QT interval corrected for heart rate using Fridericia's formula
RNA	ribonucleic acid
SAE	serious adverse event
SOP	standard operating procedure
SRC	Safety review committee
STAT	signal transducer and activator of transcription
TB	tuberculosis
TEAE	treatment-emergent adverse event
Th	T helper cell
TNF- α	tumor necrosis factor alpha
TYK	tyrosine kinase

Abbreviations and Special Terms	Definition
ULN	upper limit of normal
V_d/F	apparent volume of distribution after non-intravenous administration
WBC	white blood cell

1. PROTOCOL SUMMARY

Protocol Title: A Phase 2, Dose-Escalation, Placebo-Controlled Study of the Safety of INCB054707 in Participants With Hidradenitis Suppurativa

Protocol Number: INCB 54707-203

Objectives and Endpoints:

[Table 1](#) presents the primary and key secondary objectives and endpoints.

Table 1: Primary and Key Secondary Objectives and Endpoints

Objectives	Endpoints
Primary	
To determine the safety and tolerability of INCB054707.	
Frequency, duration, and severity of AEs, clinical laboratory test results, vital signs results, ECGs, and physical examination findings.
Key Secondary	
To determine the systemic exposure to INCB054707.	
Population PK parameters of INCB054707.
To determine the efficacy of INCB054707.	
Proportion of participants achieving a HiSCR at each visit.Proportion of participants achieving an AN count of 0 to 2 at each visit.Mean change from baseline in the HS Pain NRS scores, worst and average pain, at each visit.Mean change from baseline to Week 8 in the modified Sartorius scale score.Mean change from baseline in the number of draining fistulas count at each visit.Proportion of participants at each category of Hurley Stage at baseline and Week 8.Proportion of participants with change from baseline in Hurley Stage at Week 8.Proportions of participants in each HS-PGIC category during the treatment period.Actual measurements in HS-PGIC at each visit.

Overall Design:

[figure not shown]
[Table 2](#) presents the key study design elements. Further study details are presented after the table.

Table 2: Key Study Design Elements

Study Phase	Phase 2
Clinical Indication	HS
Population	Men and women aged 18 to 75 years with moderate to severe HS for at least 6 months
Number of Participants	The study includes 3 cohorts and approximately 36 participants will be enrolled. In each cohort, approximately 12 participants will be randomized 3:1 (INCB054707:placebo) to 1 of 2 treatment groups.
Study Design	Randomized, dose escalation, placebo-control
Estimated Duration of Study Participation	The study will consist of a screening period of up to 28 days, an 8-week treatment period, and a 30-day safety follow-up period. The estimated total duration of study participation is approximately 16 weeks for each participant.
Data Safety Monitoring Board	No

Treatment Groups and Duration:

The study design is shown in [Figure 1](#) below. The schedule of assessments is detailed in [Table 3](#).

The study includes 3 cohorts and approximately 36 participants will be enrolled. In each cohort, approximately 12 participants will be randomized to receive either INCB054707 (n = 9) or placebo (n = 3). The total duration of therapy for all enrolled participants is 8 weeks with a 30-day safety follow-up period. Cohort progression will be determined by the SRC evaluation of safety data following completion of Week 4 of all participants from a cohort (see Section [6.5.2](#)).

Table 3: Schedule of Assessments

Evaluation	Section	Screening	Treatment						Safety Follow-Up
		Day -28 to -1	Day 1 ^a	Week 1 ± 1 day	Week 2 ^b ± 3 days	Week 4 ^a ± 3 days	Week 6 ^b ± 3 days	Week 8 ^a ± 3 days (EOT)	
Administrative/screening procedures									
Informed consent	8.1.1	X							
Demography/medical history	8.1.6	X							
Inclusion/exclusion criteria	5	X	X						
Prior/concomitant medications	6.7	X	X	X	X	X	X	X	X
Serology	8.3.5.2	X							
Urinalysis	8.3.5.2	X							X
TB screening	8.3.5.2	X							
FSH ^c	8.3.5.2	X							
Pregnancy testing ^d	8.3.5.3	X	X	X	X	X	X	X	X
Contact IWRS	8.1.3	X	X	X	X	X	X	X	
Randomization to treatment arm	8.1.3		X						
Dispense study drug	6.1		X			X			
Collect study drug and assess compliance	6.4			X	X	X	X	X	
Distribute reminder cards	8.1.4	X	X	X	X	X	X	X	
Electronic diary verification	8.1.5		X	X	X	X	X	X	X
Safety procedures/assessments									
Comprehensive physical examination ^e	8.3.2	X						X	
Targeted physical examination	8.3.2		X	X	X	X	X		X
Vital signs	8.3.3	X	X	X	X	X	X	X	X
Hematology and chemistry assessments ^f	8.3.5.1, 8.6	X	X	X	X ^f	X ^f	X ^f	X	X
Lipid panel	8.3.5.1		X						X
CRP	8.3.5.1		X						X
12-lead ECG (screening) ^g	8.3.4	X							
12-lead ECG (predose and postdose) ^g	8.3.4		X			X			
12-lead ECG (predose only) ^g	8.3.4							X	
Assess AEs	8.3.1, 9	X	X	X	X	X	X	X	X

Table 3: Schedule of Assessments (Continued)

Evaluation	Section	Screening	Treatment						Safety Follow-Up
		Day -28 to -1	Day 1 ^a	Week 1 ± 1 day	Week 2 ^b ± 3 days	Week 4 ^a ± 3 days	Week 6 ^b ± 3 days	Week 8 ^a ± 3 days (EOT)	
Efficacy assessments									
Hurley Stage	8.2.1	X						X	X
AN count (HiSCR)	8.2.2	X	X	X	X	X	X	X	X
Modified Sartorius score	8.2.3		X					X	X
Record rescue lesional treatment	8.2.4			X	X	X	X	X	X
HS Pain NRS ^c	8.2.5		X	X	X	X	X	X	X
Evaluate daily analgesic use	8.2.6		X	X	X	X	X	X	X
HS-PGIC	8.2.7			X	X	X	X	X	X
DLQI	8.2.8		X	X	X	X	X	X	X
Optional photography (target area)	8.2.9		X			X		X	

^a An overnight (at least 8-hour) fast will be required at these visits. Participant will take study drug at the study sites.

^b Participants will take study drug before the study visit.

^c For confirmation of nonchildbearing status for women who are postmenopausal, defined as amenorrhea at least 12 months before screening.

^d For women of childbearing potential only. Serum test will be conducted at screening and urine test will be conducted at all other visits.

^e A brief neurological examination will also be performed.

^f If there is a potential clinically significant abnormality in chemistry or hematology assessments (particularly in platelet count) at Week 2, 4, or 6, then an unscheduled visit the following week (Weeks 3, 5, 7) to repeat the assessment is required.

^g See [Table 10](#).

^h The HS Pain NRS includes worst pain and average pain in the last 24 hours.

2. INTRODUCTION

INCB054707 is a JAK1 inhibitor. Janus kinase signaling regulates many different proinflammatory signaling pathways and is now well-recognized as a key driver for numerous inflammatory skin diseases.

2.1. Background

2.1.1. Hidradenitis Suppurativa

Hidradenitis suppurativa is a chronic disease characterized by recurrent, painful, deep-seated, rounded nodules and abscesses of apocrine gland-bearing skin. Abscesses typically rupture and release purulent drainage. Abscesses and nodules may heal with scarring and the formation of fistulas or sinus tracts ([Revuz 2009](#)). Thus, many patients with HS develop permanent sequelae of past inflammation that are only remediable through surgical excision of the involved skin areas. Onset is usually after puberty, although it is most common during the third decade of life and may persist in old age. The prevalence rate is about 1% (range: 0.2%-4%; [Jemec et al 1996](#), [Revuz et al 2008](#)). Axillary and inguinal involvement is more common in females; perianal and buttocks localizations are prevalent in males. Genetic susceptibility, smoking, and obesity are important risk factors for the development of HS. An association between HS and metabolic syndrome has recently been established ([Miller et al 2014](#)).

Hidradenitis suppurativa significantly affects healthcare costs and health-related quality of life. A recent study indicates that HS imposes a greater negative impact on quality of life than does psoriasis ([Hamzavi et al 2017](#)). Rare complications of HS include fistula formation into the urethra, bladder, rectum, or peritoneum; lymphedema of the limbs or scrotal elephantiasis; and squamous cell carcinomas of the skin originating from HS lesions.

The pathogenesis of HS has not yet been fully elucidated. It has been suggested that follicular plugging followed by the release of follicular material into the dermis are primary events that activate the immune system. Defects in host defense mechanisms as well as innate and adaptive immunity may also contribute. Unravelling which cytokines are involved has been the main objective of several studies. Recently, it has been shown that the IL-23/Th17 and IL-12/Th1 pathways are expressed in HS skin ([Schlapbach et al 2011](#)). Although TNF- α presents in inflammatory HS skin, several studies indicate that it may not be the key contributor in the pathogenesis of this disease ([Kelly et al 2015](#), [van der Zee et al 2012](#), [Moran et al 2017](#)), suggesting opportunities for other potential therapeutic targets.

2.1.2. Current Treatment and Unmet Need in Hidradenitis Suppurativa

Treatment of HS depends on the extent and activity of disease. Current European guidelines for the treatment of HS generally recommend topical clindamycin or oral tetracycline as first-line therapy for mild disease ([Gulliver et al 2016](#), [Zouboulis et al 2015](#)). For moderate to severe disease, oral clindamycin and rifampin combination therapy are used as first-line treatment, and adalimumab (TNF- α inhibitor) is used as a second-line treatment. Of note, the latter is the only

[figure not shown]
US FDA-approved systemic therapy for HS. In more severe cases with extensive scarring, surgical intervention is used to remove the nondynamic components of HS (eg, scarring, fistulas, and sinus tracts) that are not expected to respond to drug therapy. These comprise a number of surgical procedures (eg, incision and drainage, de-roofing, and excision) laser (Nd:YAG) and radiation therapy (Jemec 2012). Other systemic/pharmacologic therapies include drugs such as acitretin, isotretinoin, dapsone, antiandrogens (in female patients), intralesional injections of triamcinolone, and a number of TNF- α inhibitors (Rambhatla et al 2012).

Given that the current pharmacologic treatments are moderately effective at best, are not approved for HS (except for adalimumab), and are often associated with significant side effects, there is a need for new effective agents for the treatment of HS. Although several biologic agents are undergoing clinical investigation at this time (IL-17 inhibitors: bimekizumab and secukinumab), an oral treatment with a JAK1-inhibitor such as INCB054707 has the potential to address an unmet medical need for patients with HS.

2.1.3. JAK-STAT Signaling in Inflammatory Skin Disease

[figure not shown]
The JAK family of kinases includes JAK1, JAK2, JAK3, and TYK2. The JAK-STAT pathway is used by cytokines including ILs, interferons, and other molecules to transmit signals from the cell membrane to the nucleus. Upon engagement of extracellular ligands, intracellular JAK proteins, which associate with type I/II cytokine receptors, become activated and phosphorylate STAT proteins, which dimerize and then translocate into the nucleus to directly regulate gene expression. Among all JAK family members, JAK1 signaling relates primarily to cytokines involved in inflammation (Rawlings et al 2004).

Numerous inflammatory dermatoses are driven by soluble inflammatory mediators, which rely on JAK-STAT signaling.

To date in dermatology, psoriasis has been the most studied indication for JAK inhibitors including tofacitinib, baricitinib, and ruxolitinib. The sponsor has completed 4 clinical studies with JAK1 and JAK2 inhibitors for the treatment of psoriasis. Both topical ruxolitinib (Punwani et al 2015) and oral INCB039110 (Bissonnette et al 2013) have been associated with clinical improvement and benefit in patients with chronic plaque psoriasis.

2.2. Study Rationale

Given that TNF- α may not be the major driver for HS pathogenesis, and that there is a relatively high number of patients who do not sufficiently respond to therapy with the only approved HS medication impacting that pathway (adalimumab, a TNF- α inhibitor), there remains a significant unmet need for new treatments for HS.

2.2.1. Scientific Rationale for Study Design

Recent literature suggests that the main cytokines involved in HS pathogenesis are IL-1 β , IL-17, IL-23, IL-10, and, to a lesser extent, TNF- α (Kelly and Prens 2016). The expression and/or activity of these cytokines is profoundly regulated by the intracellular level through JAK-STAT signaling, and is primarily mediated by JAK1 (see Section 2.1.3).

[figure not shown]
[figure not shown]
[figure not shown]
[figure not shown]
[figure not shown]
[figure not shown]
[figure not shown]
[figure not shown]
[figure not shown]
[figure not shown]
[figure not shown]
[figure not shown]
[figure not shown]
[figure not shown]
[figure not shown]
[figure not shown]
[figure not shown]
[figure not shown]
[figure not shown]
[figure not shown]
[figure not shown]
[figure not shown]
[figure not shown]
[figure not shown]
[figure not shown]
[figure not shown]
[figure not shown]
[figure not shown]
[figure not shown]
[figure not shown]
[figure not shown]
[figure not shown]
[figure not shown]
[figure not shown]
[figure not shown]
[figure not shown]
[figure not shown]
[figure not shown]
[figure not shown]
[figure not shown]
[figure not shown]
[figure not shown]
[figure not shown]
[figure not shown]
[figure not shown]
[figure not shown]
[figure not shown]
[figure not shown]
[figure not shown]
[figure not shown]
[figure not shown]
[figure not shown]
[figure not shown]
[figure not shown]
[figure not shown]
[figure not shown]
[figure not shown]
[figure not shown]
[figure not shown]
[figure not shown]
[figure not shown]
[figure not shown]
[figure not shown]
[figure not shown]
[figure not shown]
[figure not shown]
[figure not shown]
[figure not shown]
[figure not shown]
[figure not shown]
[figure not shown]
[figure not shown]
[figure not shown]
[figure not shown]
[figure not shown]
[figure not shown]
[figure not shown]
[figure not shown]
[figure not shown]
[figure not shown]
[figure not shown]
[figure not shown]
[figure not shown]
[figure not shown]
[figure not shown]
[figure not shown]
[figure not shown]
[figure not shown]
[figure not shown]
[figure not shown]
[figure not shown]
[figure not shown]
[figure not shown]
[figure not shown]
[figure not shown]
[figure not shown]
[figure not shown]
[figure not shown]
[figure not shown]
In this study, the safety and tolerability of 3 doses [REDACTED] of INCB054707 will be evaluated in adult participants with moderate to severe HS and compared with placebo. A dose-escalation design has been chosen to evaluate the safety and tolerability of dose of

INCB054707 in a step-wise fashion. Placebo treatment will facilitate unbiased safety assessments and is acceptable in this patient population in the short term. Each cohort's safety data will be reviewed before advancing to the next dose level. Eight weeks study drug exposure is an adequate duration to evaluate potential adverse hematologic effects and beneficial effects in HS and to support larger subsequent studies of longer duration.

For participants experiencing bothersome symptoms related to either rapid abscess formation or secondary infection at the diseased sites, appropriate rescue treatments will be offered to immediately evacuate pus (incision and drainage), alleviate the level of inflammation (intralesional triamcinolone), or control infection (see Sections 6.7.1 and 8.2.4).

It is expected that the outcome of this study will be instrumental by informing a larger dose-ranging Phase 2b study.

2.2.2. Justification of Dose

[figure not shown]Frequency, duration, and severity of AEs, clinical laboratory test results, vital signs results, ECGs, and physical examination findings.
Secondary	
To determine the systemic exposure to INCB054707.	
Population PK parameters of INCB054707.
To determine the efficacy of INCB054707.	
Proportion of participants achieving a HiSCR at each visit.Proportion of participants achieving an AN count of 0 to 2 at each visit.Mean change from baseline in the HS Pain NRS scores, worst and average pain, at each visit.Mean change from baseline to Week 8 in the modified Sartorius scale score.Mean change from baseline in the number of draining fistulas count at each visit.Proportion of participants at each category of Hurley Stage at baseline and Week 8.Proportion of participants with change from baseline in Hurley Stage at Week 8.Proportions of participants in each HS-PGIC category during the treatment period.Actual measurements in HS-PGIC at each visit.
To assess the need for rescue lesional treatment.	
Proportion of participants requiring rescue lesional treatment.Number of interventions with rescue lesional treatment.
To assess patient-reported quality-of-life burden.	
Proportion of participants at each scoring category of DLQI at each visit.Mean change from baseline in DLQI total scores at each visit.

Table 5: Objectives and Endpoints (Continued)

Objectives	Endpoints

4. STUDY DESIGN

4.1. Overall Design

This is a Phase 2, multicenter, randomized, placebo controlled, dose escalation study to evaluate the safety of INCB054707 [REDACTED] over an 8-week treatment period in men and women aged 18 to 75 years with moderate to severe HS with a targeted enrollment of approximately 36 participants (see [Figure 1](#)).

The study includes 3 cohorts, and approximately 36 participants will be enrolled. In each cohort, approximately 12 participants will be randomized to receive either INCB054707 (n = 9) or placebo (n = 3; randomization 3:1). The total duration of therapy for all enrolled participants is 8 weeks followed by a 30-day safety follow-up period. After all participants in each cohort have completed the Week 4 study visit and assessments, a SRC will review safety data. See Section [6.5.2](#) for detail procedures for cohort review and dose escalation.

4.2. Overall Study Duration

The study will consist of a screening period of up to 28 days, an 8-week treatment period, and a 30-day safety follow-up period. The estimated total duration of study participation is approximately 16 weeks for each participant.

4.3. Study Termination

The investigator retains the right to terminate study participation at any time, according to the terms specified in the study contract. The investigator is to notify the IRB/IEC in writing of the study's completion or early termination, send a copy of the notification to the sponsor or sponsor's designee, and retain 1 copy for the site study regulatory file.

The sponsor may terminate the study electively or if required by regulatory decision or upon advice of the SRC. If the study is terminated prematurely, the sponsor or designee will notify the investigators, the IRBs/IECs, and regulatory bodies of the decision and reason for termination of the study. The SRC will recommend termination of the study if warranted, as described in Section [6.5.2](#).

5. STUDY POPULATION

Deviations from eligibility criteria are not allowed because they can potentially jeopardize the scientific integrity of the study, regulatory acceptability, and/or participant safety. Therefore, adherence to the criteria as specified in the Protocol is essential. Prospective approval of Protocol deviations to recruitment and enrollment criteria, also known as Protocol waivers or exemptions, are not permitted.

5.1. Inclusion Criteria

Participants are eligible to be included in the study only if all of the following criteria apply:

1. Men and women aged 18 to 75 years at the time of consent.
2. Diagnosis of HS (confirmed by a dermatologist) with a disease duration of at least 6 months before screening.
3. Stable course of HS for at least 90 days before screening, as determined by the investigator.
4. HS lesions present in at least 2 distinct anatomic areas, 1 of which must be Hurley Stage II (ie, recurrent abscessed with tract formation and cicatrization; single or multiple, widely separated lesions) or Hurley Stage III (ie, diffuse or near diffuse involvement, or multiple interconnected tracts and abscesses across the entire area) at screening.
5. Total AN count of at least 3 at screening and baseline.
6. Willingness to avoid pregnancy or fathering children based on the criteria below:
 - a. Male participants must agree to take appropriate precautions to avoid pregnancy (with at least 99% certainty) from screening through 90 days after the last dose of study drug. Male participants must also refrain from donating sperm during this period. Permitted methods that are at least 99% effective in preventing pregnancy (see [Appendix A](#)) should be communicated to the participant and his understanding confirmed.

- b. Women of childbearing potential must have a negative serum pregnancy test at screening and a negative urine pregnancy test before the first dose on Day 1 and must agree to take appropriate precautions to avoid pregnancy (with at least 99% certainty) from screening through safety follow-up. Permitted methods that are at least 99% effective in preventing pregnancy (see [Appendix A](#)) should be communicated to the participants and their understanding confirmed.
- c. Women of nonchildbearing potential (ie, surgically sterile [hysterectomy, bilateral oophorectomy, or bilateral salpingectomy] OR postmenopausal, defined as ≥ 12 months of amenorrhea before screening without an alternative medical cause, confirmed by FSH levels at screening) are eligible.

5.2. Exclusion Criteria

Participants are excluded from the study if any of the following criteria apply:

- 1. Women who are currently pregnant or lactating.
- 2. Presence of > 20 draining fistulas at screening and baseline.
- 3. Participants with concurrent conditions or history of other diseases, as follows:
 - a. Any clinically significant medical condition other than HS, as determined by the investigator, that is not adequately controlled with appropriate treatment.
 - b. Any other active skin disease or condition (eg, bacterial, fungal, or viral infection) that may interfere with the course, severity, or assessments of HS.
 - c. Active systemic viral infection or any active viral infection that, based on the investigator's clinical assessment, make the participant an unsuitable candidate for the study.
 - d. Current herpes zoster infection, a history of recurrent herpes zoster, a history of disseminated herpes simplex, or a history of herpes zoster.
 - e. History of or ongoing serious illness or medical, physical or psychiatric condition(s) that – in the investigator's opinion – would interfere with full participation in the study, including administration of study drug and attending required study visits; pose a significant risk to the participant; or interfere with interpretation of study data.
 - f. Albinism.
- 4. Prolonged QT interval corrected for heart rate using Fridericia's formula (QTcF), defined as ≥ 450 msec.

Note: Prolonged QTcF values of ≥ 450 msec at screening are to be confirmed by performing 2 additional ECGs and averaging the results to determine whether the averaged value meets the exclusion criterion.

- 5. Positive test result for TB from the QuantiFERON-TB Gold test, or T-SPOT.TB test at screening (or, if two indeterminate tests, then as evaluated by a purified protein derivative test with a result of < 5 mm of induration within 3 months of screening).

6. A history of active TB (treated or untreated) or a history of untreated latent TB.

Note: If the participant has possible evidence of a latent TB infection, the participant must have documented completion of an adequate course of therapy for latent TB and provide recent (within 3 months) posteroanterior and lateral view chest X-rays without changes suggestive of active or latent TB, before baseline.

7. Positive serology test results for HIV, HBsAg, HBV core antibody, or HCV (HCV-antibody with positive HCV-RNA) at screening.

8. Decreased blood cell counts at screening, defined as follows:

- a. Leukocytes $< 3.0 \times 10^9/\text{L}$ ($< 2.5 \times 10^9/\text{L}$ for participants who are African-American).
- b. ANC $< 1.5 \times 10^9/\text{L}$.
- c. Lymphocytes $< 0.8 \times 10^9/\text{L}$.
- d. Hemoglobin $< 10 \text{ g/dL}$.
- e. Platelets $< 150 \times 10^9/\text{L}$.

9. Severely impaired liver function (Child-Pugh Class C) or ALT or AST levels $\geq 1.5 \times \text{ULN}$ at screening.

10. Impaired renal function with serum creatinine $> 1.5 \text{ mg/dL}$ at screening.

11. Use of the following medications:

- a. Previous use of JAK inhibitors, systemic or topical (eg, ruxolitinib, tofacitinib, baricitinib, filgotinib, lestaurtinib, and pacritinib).
- b. Previous use of adalimumab or any other TNF- α treatment within 12 weeks or 5 half-lives (whichever is longer) before baseline.
- c. Use of any investigational or experimental treatments within 12 weeks or 5 half-lives (whichever is longer) before baseline.
- d. Systemic immunosuppressive or immunomodulating drugs (eg, oral or injectable corticosteroids, methotrexate, cyclosporine, and azathioprine) within 4 weeks or 5 half-lives (whichever is longer) before baseline.
- e. Other systemic therapies for HS (eg, retinoids and antiandrogens) with potential therapeutic impact for HS within 4 weeks or 5 half-lives (whichever is longer) before baseline.
- f. Surgical, laser, or IPL intervention in area with HS lesion within 4 weeks before baseline.
- g. Systemic anti-infectives (eg, antibiotics, antivirals, antifungals) within 4 weeks, except as described in Section 6.7.1.1 for antibiotic therapy, or topical anti-infectives on HS lesions (eg, antibiotics, antivirals, antifungals) within 2 weeks before baseline.
- h. Received live vaccine within 6 weeks before baseline or planning to receive live vaccine during the course of the study or within 6 weeks after EOT.

- i. Topical antiseptic washes, creams, soaps, ointments, gels, and liquids containing antibacterial agents to treat HS, except those listed in Sections [6.7.1.3](#) and [6.7.1.4](#), within 2 weeks before baseline.
- j. Potent systemic CYP3A4 inhibitors and inducers (see Study Manual) or fluconazole within 2 weeks or 5 half-lives (whichever is longer) before baseline.
Note: Topical agents with limited systemic availability are permitted.

12. Known or suspected allergy to INCB054707 or any component of the study drug.

13. Known history of clinically significant drug or alcohol abuse in the last year before baseline.

14. For participants consenting to biopsies only:

- a. Participant has a history of an allergic reaction or significant sensitivity to lidocaine or other local anesthetics.
- b. Participant has a history of hypertrophic scarring or keloid formation in scars or suture sites.
- c. Participant is taking anticoagulant medication, such as heparin, low molecular weight-heparin, warfarin, and antiplatelets (nonsteroidal anti-inflammatory drugs and low-dose aspirin will be allowed), or has a contraindication to skin biopsies.

15. Inability or unlikelihood of the participant to comply with the dose schedule and study evaluations, in the opinion of the investigator.

16. Inability of the participant (or parent, guardian, or legally authorized representative) to comprehend or unwilling to sign the ICF.

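### Exclusion criterion 5 contradicts itself: it opens by excluding a positive TB test, but its skin-test branch names induration below 5 mm as meeting the exclusion

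*Protocol*

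**What the plan says.** Protocol 5.2 sets the direction for the whole list: "Participants are excluded from the study if any of the following criteria apply". Meeting a criterion therefore means exclusion.

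Criterion 5 opens with "Positive test result for TB from the QuantiFERON-TB Gold test, or T-SPOT.TB test at screening". A parenthesis follows, attached by the word or, for participants with two indeterminate blood tests: "as evaluated by a purified protein derivative test with a result of < 5 mm of induration within 3 months of screening".

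Criterion 6 is separate and concerns history: "A history of active TB (treated or untreated) or a history of untreated latent TB". Its note asks for documented completed treatment and recent clear chest X-rays where latent infection is suspected. It gives no skin-test threshold.

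Protocol Section 5 adds that "adherence to the criteria as specified in the Protocol is essential".

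**The concern.** The opening of criterion 5 excludes people whose TB test is positive. The parenthesis puts a low skin-test reading, which includes no reaction at all, in the same excluded group. The two halves of one sentence point in opposite directions, and this is an operative eligibility rule that sites must apply before randomization.

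Three things are at stake. First, a site that follows the words turns away participants with little or no reaction for no reason the criterion itself supports. Second, the study is multicenter, and sites may resolve the conflict differently, so eligibility would not be uniform. SAP Appendix A plans a listing of inclusion and exclusion violations (Listing 1.1.2), and its content would depend on which reading is used. Third, the study drug is a JAK1 inhibitor and serious infections are adverse events of special interest (Protocol 9.5). A TB screen that does not catch larger reactions in its fallback branch is weaker than the criterion's opening implies.

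**Working it through.** No sample-size, power or event figure enters this point, so there is no figure of the plan to reproduce. The check is a reading of the text, followed by one line of arithmetic for scale.

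**Step 1: what the branch does as written.** For a participant with two indeterminate blood tests, meeting the criterion means exclusion.

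| Skin-test result | Criterion 5 as worded | Consequence under criterion 5 |
|---|---|---|
| 0 to < 5 mm | met | excluded |
| 5 mm or more | not met | not excluded |

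**Step 2: compare with the opening.** The opening excludes positive results. One premise is not written in the Protocol: that larger induration points towards a positive skin test, not away from it. Given that, any rule based on positive results must exclude from some value upwards, whatever the value. The branch excludes from a value downwards. The conflict is one of direction and does not depend on where the cut-off lies.

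**Step 3: see how the rest of the list uses thresholds.** Criterion 4 (QTcF) and every item of criterion 8 (blood counts) state the value that excludes. A site reading criterion 5 in the same way would take < 5 mm as the excluding value.

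**Step 4: look for text that settles it.**
- Criterion 6 and its note give no skin-test direction.
- Protocol 8.3.5.2 lists TB screening among the screening tests and refers sites to the Laboratory Manual.
- SAP 8.3.2 names only the QuantiFERON-TB Gold test.
- Protocol Table 11 is not in the text available for this review and could not be checked.

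Nothing available resolves the conflict.

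**Step 5: scale.** The documents do not say how many participants will have two indeterminate tests. Assume 0% to 5% and take the planned enrollment of about 36 as the base:
- 0.00 × 36 = 0
- 0.05 × 36 = 1.8, or about 2

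This counts participants who reach the skin-test branch. It does not count wrong decisions. It is only an order of magnitude, because the rule acts at screening and the documents give no number screened.

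**The case against.** **The parenthesis may describe the result that clears a participant.** This is plausible as a drafting history. The text does not say it, however: nothing in the clause marks the result as negative or as permitting entry, and the word or ties it to the exclusion. The objection shows that the sentence is garbled, and so it supports clarifying it.

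**Other criteria still protect participants.** This stands in part. Someone with a larger reaction may fall under the criterion 6 note, although the Protocol does not define what counts as evidence of latent infection. Criterion 3e lets the investigator exclude for significant risk. A reader might infer that the text, followed literally, simply enrols people with TB infection. The documents do not support that, because these further gates remain.

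**Unseen manuals may cover indeterminate results.** This is possible for the Laboratory Manual and Table 11. It limits what can be said about how sites will act, but not about what criterion 5 says.

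Two stronger readings are tempting and should not be drawn:

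- **That a site reading the criterion sensibly is formally deviating**, since Section 5 says "Prospective approval of Protocol deviations to recruitment and enrollment criteria, also known as Protocol waivers or exemptions, are not permitted". That rule bars approved departures from a criterion. It does not say how to read a criterion whose halves conflict, and a site that lets the opening govern is following words that are in it.
- **That resulting infections would drive the escalation decision.** For one to count, a participant would need two indeterminate tests, a larger reaction and passage through criteria 3e and 6. The participant would then need assignment to active drug and a serious infection by Week 8 without a clear cause unrelated to study drug (Protocol 6.5.1). Escalation ends only with 3 or more such participants treated with INCB054707 in one cohort, or if the drug is judged not tolerable (6.5.2). The assumed 0-2 is spread over three cohorts and counts people reaching the branch. The chain is speculative.

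**Conclusion.** The contradiction is real and is in the wording of criterion 5 itself. Taken literally, the branch for two indeterminate tests excludes little or no reaction and leaves a larger one unexcluded by that criterion. Confidence is high on the wording and lower on what sites would do with it.

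The effect is small in number. It is confined to participants with two indeterminate blood tests, 0-2 under the 0-5% assumption, and a wrong admission would be rarer still. It changes neither the sample size nor any efficacy analysis. It still merits correction because it is an eligibility rule with a safety purpose that gives the wrong direction as written.

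**What to change.** In the next amendment, rewrite criterion 5 so that its two halves agree:

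- State separately, for a participant with two indeterminate blood tests, which skin-test result excludes and which permits entry.
- Say how that result relates to criterion 6 and its note, so that the two TB criteria cannot give different answers for the same person.
- If the Laboratory Manual covers indeterminate results, bring it into line.

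The cut-off itself is for the sponsor to confirm; none is proposed here. The cost is one line in the amendment and a clarification letter to sites. No analysis needs to be re-planned.
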